---

## DOCUMENT HISTORY

Protocol	Approval Date (Version)
Amendment 01	See Sponsor's Protocol Approval Page (Version 2.0)
Original	10 Oct 2023 (Version 1.0)

	Protocol 812P413	
	Page 4 of 61	Version 2.0

[figure not shown]
[figure not shown]

## 1. List of Abbreviations

Abbreviation	TERM/DEFINITION
ADHD	Attention-Deficit/Hyperactivity Disorder
AE	Adverse Event
AISRS	Adult ADHD Investigator Symptom Rating Scale
ASRSv1.1-SC	Adult ADHD Self-Report Scale v1.1 Symptoms Checklist
ATC	Anatomical Therapeutic Chemical
BP	Blood pressure
BRI	Behavioral Regulation Index
BRIEF-A	Behavior Rating Inventory of Executive Function-Adult Version
CFR	Code of Federal Regulations
CGI-C	Clinical Global Impression of Change Scale
CGI-S	Clinical Global Impression of Severity Scale
ClinRO	Clinician-reported outcome
COACH	Clinical Oversight and Coordination Hub
CPM	Clinical Project Manager
CRF	Case Report Form
C-SSRS	Columbia Suicide Severity Rating Scale
DSM-5	Diagnostic and Statistical Manual; fifth edition
EC	Ethics Committee
eCRF	Electronic Case Report Forms
EDC	Electronic data capture
eIC	Electronic informed consent
EOS	End of study
ER	Extended-release
FDA	Food and Drug Administration
FOCP	Female of childbearing potential
GAD	General Anxiety Disorder
GAD-7	General Anxiety Disorder 7-item scale
GCP	Good Clinical Practice
GEC	Global Executive Composite
HAM-A	Hamilton Anxiety Rating Scale
HI	Hyperactivity/Impulsivity
ICH	International Council on Harmonisation
IA	Inattention
IRB	Institutional Review Board
IUD	Intrauterine device
MADRS	Montgomery-Åsberg Depression Rating Scale
MAOI	Monoamine oxidase inhibitors
MDD	Major Depression Disorder
MedDRA	Medical Dictionary for Regulatory Activities

	Protocol 812P413	
	Page 9 of 61	Version 2.0

mg	Milligrams
MI	Metacognition Index
MINI-AS	Mini-International Neuropsychiatric Interview for ADHD Studies
NRI	Norepinephrine reuptake inhibitor
OCD	Obsessive compulsive disorder
PHQ-8	Patient Health Questionnaire-8 item
PI	Principal Investigator
PRO	Patient-reported outcome
PSQI	Pittsburgh Sleep Quality Index
PT	Preferred Term
PTSD	Post-traumatic stress disorder
QA	Quality Assurance
QC	Quality Control
OCD	Obsessive Compulsive Disorder
QD	Once a day
RMCH	Reproductive/Menstrual Cycle History Questionnaire
SAE	Serious Adverse Event
SIGH-A	Structured Interview Guide for the Hamilton Anxiety Scale
SIGMA	Structured Interview Guide for the Montgomery-Åsberg Depression Rating Scale
SM	Study medication
SOC	System Organ Class
SOE	Schedule of Events
SOP	Standard Operating Procedure
Sub-I	Sub-Investigator
TEAE	Treatment-emergent Adverse Event
UAP	Unanticipated problems
US	United States
WPAI:SHP	Work Productivity and Activity Impairment: Specific Health Problem Questionnaire

	Protocol 812P413	
	Page 10 of 61	Version 2.0

## 2. Protocol Synopsis

### Title

A Phase IV, Open-label, Decentralized Clinical Trial to Evaluate the Efficacy and Safety of Qelbree in Adults with Attention-Deficit/Hyperactivity Disorder (ADHD) and Mood Symptoms

### Study Description:

This is a Phase IV, open-label, decentralized clinical trial to evaluate the efficacy and safety of Qelbree in adults with ADHD and mood symptoms. Adults 18 years and older will be recruited into this study. Participants will be recruited using digital and social media advertising, and referrals from physicians' existing patient pool. Individuals who are pre-qualified will be sent an email invitation to download the study app and contacted to schedule a screening televisit. Once eligibility is confirmed and participants are enrolled, study medication will be shipped. The treatment period will last for up to a total of 14 weeks. Participants will be assessed for compliance and specific outcomes during the treatment period

### Study Objectives

#### Primary Efficacy Objective

The primary objective of this study is to evaluate the efficacy of Qelbree as a monotherapy and/or as an adjunctive therapy for ADHD symptoms in adults with ADHD and comorbid mood symptoms as measured by the clinician-rated ADHD Investigator Symptom Rating Scale (AISRS).

#### Secondary Efficacy Objectives

[figure not shown]
The secondary objectives of this study are to evaluate the effect of Qelbree as a monotherapy and/or as an adjunctive therapy in adults with ADHD and comorbid mood symptoms on:

- Inattention and Hyperactivity/Impulsivity symptoms as measured by the clinician-rated AISRS.
- ADHD symptoms as measured by self-rated Adult ADHD Self-Report Scale Symptoms Checklist (ASRSv1.1-SC).
- Inattention and Hyperactivity/Impulsivity symptoms as measured by the self-rated ASRSv1.1-SC
- Global severity of ADHD symptoms as measured by Clinical Global Impression of Severity (CGI-S) scale
- Global change of ADHD symptoms as measured by the Clinical Global Impression of Change (CGI-C) scale
- Depressive symptoms as measured by the clinician-rated Structured Interview Guide for the Montgomery and Åsberg Depression Rating Scale (SIGMA) and by the self-rated Patient Health Questionnaire 8-Item (PHQ-8)

- Anxiety symptoms as measured by the clinician-rated Structured Interview Guide for the Hamilton Anxiety Scale (SIGH-A) and the self-rated General Anxiety Disorder 7-Item (GAD-7)
- Executive Function as measured by the Behavior Rating Inventory of Executive Function-Adult Version (BRIEF-A), Self-Report
- Aspects of functioning in daily life (work productivity and regular activities) as measured by the Work Productivity and Activity Impairment: Specific Health Problem (WPAI:SHP) Questionnaire
- Sleep as measured by the self-rated Pittsburgh Sleep Quality Index (PSQI)

**Secondary Safety Objective**

To evaluate the safety of Qelbree as a monotherapy and/or as an adjunctive therapy in adults with ADHD and comorbid mood symptoms.

**Exploratory Objective****Study Endpoints****Primary Efficacy Endpoint**

- Change from baseline in AISRS Total score by visit

[figure not shown]
**Secondary Efficacy Endpoints**

- Change from baseline in AISRS Inattention and Hyperactivity/Impulsivity Subscale scores by visit
- Change from baseline in ASRSv1.1-SC Total score by visit
- Change from baseline in ASRSv1.1-SC Inattention and Hyperactivity/Impulsivity Subscale scores by visit
- Change from baseline in CGI-S score by visit
- CGI-C score by visit
- Change from baseline in MADRS Total Score at Week 14/EOS
- Change from baseline in PHQ-8 Total Score by visit
- Change from baseline in HAM-A Total Score at Week 14/EOS
- Change from baseline in GAD-7 Total Score by visit
- Change from baseline at Week 14/EOS in BRIEF-A T-score for:
  - i. Global Executive Composite (GEC)
  - ii. Behavioral Regulation Index (BRI)
  - iii. Metacognition Index (MI)

- Change from baseline in the WPAI:SHP:
  - absenteeism percentage by visit
  - presenteeism percentage by visit
  - work productivity percentage by visit
  - regular activity percentage by visit
- Change from baseline at Week 14/EOS in the PSQI global score

**Secondary Safety Endpoints**

- Adverse events (AEs)
- Change from baseline in blood pressure, pulse rate, and weight
- Suicidality using the Columbia Suicide Severity Rating Scale (C-SSRS)

**Exploratory Endpoints****Study Population**

Adults ≥18 years of age with ADHD (primary diagnosis) and Mood Symptoms will be screened for eligibility. Up to 750 adults will be enrolled (defined as having signed ICF and taken at least 1 dose of Qelbree). Based on a dropout rate of 33%, up to 500 participants will complete the study.

**Study Sites**

Single, decentralized site in the United States

**Study Duration**

Following the Screening Period (up to 4 weeks), eligible participants will be treated with Study medication for up to 14 weeks (Treatment Period). The total study duration between informed consent and the end of the Treatment Period is approximately 18 weeks.

**Description of Study Treatment**

Study Medication (SM): Qelbree [viloxazine extended-release capsules; SPN-812] 100 mg, 150 mg, and 200 mg capsules.

Dosing: 200 mg once daily (QD) during Week 1; and 400 mg QD Week 2 onwards. Dosage may be adjusted/titrated in increments of up to 200 mg weekly to the maximum recommended dosage of 600 mg once daily, depending on response and tolerability.

Reference Therapy: None

Route of administration: Orally, with or without food. Can be swallowed intact (whole) or contents of the capsule can be sprinkled over a teaspoonful of pudding/applesauce that is consumed entirely. See [Section 8.2](#) for further details.

### Inclusion Criteria

To be eligible for participation in this study, a participant must meet all of the following criteria:

1. Is male or female,  $\geq 18$  years of age.
2. Is willing and capable of providing and signing electronic informed consent.
3. Has a primary diagnosis of ADHD based on the Diagnostic and Statistical Manual of Mental Disorders; Fifth Edition, Text Revision (DSM-5-TR) as confirmed with the Mini-International Neuropsychiatric Interview for ADHD Studies (MINI-AS).
4. Has an AISRS Total score  $\geq 24$  at Screening.
5. Has a CGI-S score  $\geq 3$  at Screening.
6. Has a MADRS (SIGMA) Total score  $> 22$  at Screening and/or HAM-A (SIGH-A) Total score  $> 22$  at Screening.
7. If potential participant is a biological female, one of the following (a, b, or c) must be met:
  - a. Has undergone menopause, defined as a biological female who reports amenorrhea for at least 12 consecutive months prior to providing informed consent.
  - b. Is a non-pregnant Female of Childbearing Potential (FOCP) who is not seeking fertility treatment during the study and agrees to use one of the following acceptable birth control methods beginning 14 days prior to the first dose of study medication, throughout the study while taking study medication, and for 7 days following the last dose of study medication:
    - i. Hormonal contraceptive
    - ii. Barrier method: simultaneous use of male condom and diaphragm or cervical cap with spermicidal foam/gel/film/cream/suppository
  - c. Has had bilateral tubal ligation, hysterectomy, bilateral oophorectomy (permanently sterilized) at least 6 months prior to providing informed consent.
8. If potential participant is a biological male, one of the following must be met:
  - a. Is capable of having children and agrees to use 2 methods of contraception beginning 14 days prior to the first dose of study medication, throughout the study while taking study medication, and for 7 days following the last dose of study medication.
  - b. Has had sterilization surgery (permanently sterilized) at least 6 months prior to providing informed consent.
9. Owns a functioning smartphone device, has access to an internet connection (Wi-Fi or data plan), is willing to download and use the study mobile app throughout the study, and is willing to have visual telemedicine appointments (televisits) at times designated in the study protocol.

### Exclusion Criteria

A participant who meets any of the following criteria will be excluded from participation in the study:

1. Has a history of substance use disorder (alcohol, opioids, etc.) within the last 6 months prior to providing informed consent with exception of nicotine and cannabis.
2. Is currently taking or has taken Qelbree for treatment of ADHD in the last 3 months or is currently taking another non-stimulant medication for treatment of ADHD, like atomoxetine (Strattera), Clonidine (Catapres, Kapvay) or Guanfacine (Tenex, Intuniv). Stimulant medications for ADHD and most medications for mood symptoms (symptoms of depression and/or anxiety) are allowed.
3. Is taking a prohibited concomitant medication per the Qelbree prescribing information.
4. Is a FOCP who is pregnant, nursing, sexually active with a male partner and not willing to use one of the acceptable birth control methods throughout the study and/or is seeking fertility treatment.
5. Has a history of moderate or severe head trauma or other neurological disorder or systemic medical disease that, in the Investigator's opinion, is likely to affect central nervous system functioning. This would include participants with:
  - a. A current diagnosis of a major neurological disorder; or
  - b. Seizures, seizure disorder or seizure-like events; or a history of seizure disorder within the immediate family (siblings, parents); or
  - c. Encephalopathy
6. Has attempted suicide within the 6 months prior to the C-SSRS assessment at Screening, or is at significant risk of suicide, either in the opinion of the Investigator or defined as a "yes" to suicidal ideation questions 4 or 5 or answering "yes" to suicidal behavior on the C-SSRS within the 6 months prior to the C-SSRS assessment at Screening.
7. Is currently participating in another clinical trial or has participated in a clinical trial within the 60 days prior to providing informed consent.
8. Has any history of schizophrenia, schizoaffective disorder, or bipolar disorder, or has any other psychiatric disorders in the Investigator's clinical judgement would interfere with their ability to participate in the study.
9. Has any unstable, clinically significant cardiovascular condition that in the Investigator's clinical judgement would preclude their participating in the study.
10. Has any disease or taking any medication that could, in the Investigator's opinion, interfere with the assessments of safety, tolerability, or efficacy, or interfere with study conduct or interpretation of results.
11. History of unexplained loss of consciousness, unexplained syncope, unexplained irregular heartbeat or palpitations or near drowning with hospital admission.
12. In the Investigator's opinion, is unlikely to comply with the protocol or is unsuitable for any other reason.

	Protocol 812P413	
	Page 15 of 61	Version 2.0

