### 9.3 Questionnaires

#### 9.3.1 Reproductive/Menstrual Cycle History (RMCH) Questionnaire

All biologically female participants will be asked about timing of menarche, history of pregnancies, and current reproductive status at Screening. Those biologically female participants who are of childbearing potential will also be asked questions about their menstrual cycle in the past year at Screening. Those biologically female participants who are not of childbearing potential will be asked questions about when their menses stopped and the reason at Screening. At each Televisit FOCs will report the date of their last menses (RMCH Questionnaire's Menstrual-Question #5).

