#### 9.5.7 Pregnancy Reporting

Participants who self-report pregnancy will be excluded from the study at screening. If the participant reports being pregnant after enrollment, they will be withdrawn from the study and a Pregnancy Reporting Form will be filled out by the PI or designee and the Sponsor will be alerted of the pregnancy. Participants that become pregnant after enrollment and have taken at least one dose of Qelbree, will be followed until the outcome of the pregnancy is known.

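### Exclusion 4 bars nursing only in females of childbearing potential, so no specific criterion excludes a nursing woman who enters under inclusion 7a or 7c

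*Protocol*

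**What the plan says.** Exclusion 4 begins "Is a FOCP who is pregnant, nursing, sexually active with a male partner and not willing to use" one of the permitted contraceptive methods, and ends with seeking fertility treatment. The synopsis and Section 7.2 carry the same text, so neither corrects the other.

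Inclusion 7 applies to every biological female and is met if "one of the following (a, b, or c) must be met":

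- 7a is menopause, "defined as a biological female who reports amenorrhea for at least 12 consecutive months prior to providing informed consent".
- 7b begins "Is a non-pregnant Female of Childbearing Potential (FOCP) who is not seeking fertility treatment during the study" and adds a contraception requirement.
- 7c reads "Has had bilateral tubal ligation, hysterectomy, bilateral oophorectomy (permanently sterilized) at least 6 months prior to providing informed consent".

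The abbreviation list expands FOCP as "Female of childbearing potential". Neither document gives an operational definition.

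Section 9.3.1 describes the Reproductive/Menstrual Cycle History (RMCH) questionnaire. All biological females are asked at Screening about menarche, past pregnancies and present reproductive status. It then treats women outside the FOCP group separately: "Those biologically female participants who are not of childbearing potential will be asked questions about when their menses stopped and the reason at Screening".

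On pregnancy, Section 9.5.7 adds a rule that does not depend on FOCP status: "Participants who self-report pregnancy will be excluded from the study at screening".

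**The concern.** Childbearing potential bears on the risk of becoming pregnant and on the need for contraception. Whether a woman is breastfeeding does not depend on it. By listing nursing in exclusion 4, the sponsor has decided that nursing is a reason not to enrol. Placing the word inside a clause limited to FOCPs means that two women who are both nursing are treated differently because one of them has had, for example, a tubal ligation.

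At stake is whether an exclusion the sponsor already chose to make works for everyone it appears meant for. A woman it misses could take study medication for up to 14 weeks while nursing. No endpoint, analysis population or estimate is involved.

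**Working it through.** There is no figure to reproduce. The check is a comparison of the criteria and of the procedures that could support them.

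**Step 1: which limbs of exclusion 4 depend on FOCP status.** The clause opens by requiring that the participant be a FOCP. Pregnancy, nursing, refusal of contraception and fertility treatment all follow from that opening, so a woman who is not a FOCP meets none of them.

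**Step 2: how nursing is handled on each inclusion route.**

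| Route | Condition for entry | Names FOCP? | Nursing condition in the route? | Reached by exclusion 4 if nursing? |
|---|---|---|---|---|
| 7a | Reported amenorrhea, at least 12 months | No | No | No |
| 7b | Non-pregnant FOCP using contraception | Yes | No | Yes |
| 7c | Sterilized at least 6 months before consent | No | No | No |

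The last column assumes that women entering by 7a or 7c are not FOCPs. This is inferred from the three-way structure of inclusion 7 and from the separate treatment of the two groups in Section 9.3.1.

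**Step 3: concrete cases.**

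- 7c: a woman who had a tubal ligation at delivery at least 6 months before consent and is still breastfeeding satisfies 7c and falls outside exclusion 4.
- 7a: menopause is defined by reported amenorrhea alone, with no age limit and no required cause. Read literally, a pregnancy followed by some months of lactational amenorrhea could reach 12 months.

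**Step 4: other places that might exclude her.**

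- Nursing or lactation appears in no other criterion or procedure in the Protocol or SAP.
- Exclusion 10 concerns diseases and medications and does not clearly reach nursing.
- Pregnancy has checks outside exclusion 4: the non-pregnant condition in 7b, urine tests for FOCPs, and Section 9.5.7 for any participant. Nursing has no counterpart to these.
- The Televisit 1a list in Section 6.1.1 has no nursing item. It does include medical and social history and the RMCH.
- Exclusion 12 lets the Investigator turn away anyone judged unsuitable on other grounds. This is a criterion and could be used, but it is discretionary.

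**Result.** No specific criterion excludes a nursing woman who enters by 7a or 7c. Exclusion 12 can.

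**The case against.** The strongest reply has four parts.

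1. **Exclusion 12 is a criterion.** A reader might infer that such a woman passes every criterion and will be dosed. The documents do not support that, because the Investigator can exclude her. This stands, and it limits the point to the absence of a specific rule.

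2. **Screening may find her.** Section 9.3.1 puts past pregnancies and present reproductive status to all biological females, and for women not of childbearing potential it also asks why menses stopped. A recent delivery should surface before dosing. The RMCH form itself is not in the documents, so it cannot be said that it lacks a nursing item. This also stands. What remains is that, once nursing is known, no stated rule says what follows.

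3. **FOCP is undefined.** That a 7c woman is not a FOCP is a strong inference and not an explicit rule. This is correct, but the missing definition is a further reason to clarify the clause.

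4. **Neither harm nor frequency is documented.** The risk sections (3.3.1 to 3.3.3) do not discuss lactation or infant exposure, and Section 8.2.3 refers to the prescribing information for warnings. A reader might also want to count exposed infants. An assumed prevalence of 0.1% to 0.5% among 750 participants gives 750 × 0.001 = 0.75 to 750 × 0.005 = 3.75. Nothing in the documents supports that range, and the 750 includes men. The count could be zero and should not be used to grade the point.

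The remote setting adds little to the concern. Nursing status is learned by asking, whether by televisit or in person.

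**Conclusion.** The point holds as a gap in the wording of a safety exclusion. Exclusion 4 makes nursing conditional on being a FOCP, and inclusion 7 provides two routes, 7a and 7c, that do not require it. For women entering by those routes, exclusion for nursing depends on Investigator judgement under exclusion 12, possibly prompted by the reproductive history.

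This rests on two readings: that FOCP means the women described in 7b and not those in 7a or 7c, and that the sponsor did not deliberately confine the nursing bar to FOCPs. The first is strongly implied by the documents. The second is for the sponsor to confirm.

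Severity is minor. The number of women affected is unknown and probably very small, the documents give no basis for sizing harm to an infant, and no efficacy analysis changes.

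**What to change.** Reconcile inclusion 7 with exclusion 4, in the synopsis and in Sections 7.1 and 7.2, by stating whether the nursing exclusion is meant to apply regardless of childbearing potential.

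- If it is, separate nursing from the FOCP clause in both copies of exclusion 4 so that it stands as its own condition for biological females. Record nursing status for all biological females at Televisit 1a, either as an added question or by confirming that the RMCH form already asks it.
- If it is not, say so, so that the limitation to FOCPs is seen to be intended.

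The cost is one line of criteria text in each of two places and at most one yes/no screening question. Recruitment loss would be negligible, and the SAP analyses need no change.

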## 3. Introduction and Background

### 3.1 Study Rationale

Attention-deficit/hyperactivity disorder (ADHD) is one of the most common childhood disorders that can continue through to adolescence and into adulthood. Symptoms include difficulty staying focused and paying attention, difficulty controlling behavior, and hyperactivity (over-activity). The overall prevalence of ADHD in adults is between 2.5% and 6.7% with it being more common in men than women ([Abdelnour et al., 2022](#)). A majority of adults with ADHD also experience psychiatric comorbidities, particularly mood disorder symptoms, like depression and anxiety ([Kessler et al., 2006](#); [Kolar et al., 2008](#)). Medication treatment for both ADHD and any comorbid psychiatric disorders can be challenging.

While there is no cure for ADHD, available treatments aim to reduce symptoms and improve functioning. Qelbree, viloxazine extended-release capsules (SPN-812), is a selective norepinephrine reuptake inhibitor indicated for the treatment of ADHD in adults and pediatric patients 6 years and older. It is the first novel, non-stimulant option FDA-approved for adults with ADHD in the last twenty years.

The active substance in Qelbree is viloxazine, whose mechanism of action is still not fully understood. Viloxazine was previously marketed in several European countries as an antidepressant in an immediate-release (IR) product ([Findling et al., 2021](#)). The efficacy and safety of Qelbree was evaluated for the treatment of ADHD in children ([Johnson et al., 2020](#); [Nasser et al., 2020](#); [Nasser et al., 2021a](#)), in adolescents ([Nasser et al., 2021b](#); [Nasser et al., 2021c](#)) and in adults ([Nasser et al., 2022](#)). In these trials including the adult trial, participants were excluded for other psychiatric disorders, including depression and anxiety.

To date no evaluation of Qelbree has been conducted in adults with ADHD and mood symptoms, as well as those receiving concurrent medication treatment for mood symptoms. This study will evaluate the efficacy and safety of Qelbree in adults with ADHD and mood symptoms in an open-label, real-world setting.

